The primary analysis will compare uptake of PrEP by looking at the medical charts of the participants and self-reported behaviors of PrEP usage at the 3, 6, and 12 month visits between the study arms. Changes in self-reported adherence (verification with clinical chart abstraction, including lab tests for serum levels of medications), sexual behavior adjustment, post-incarceration contextual variables, and substance use will also be examined. Moreover, group differences in PrEP uptake, time-to-uptake, and number of PrEP clinic appointments kept will be compared. All analyses will use two-tailed tests of significance, with significance at alpha = 0.05. We will use generalized linear models with properly chosen link functions to analyze longitudinal data for each study aim. These models will be estimated with generalized estimating equations that use robust standard error estimates^{57,58}; they provide an extension of regression analysis to the case of correlated or repeated observations and allow for the inclusion of categorical and count-dependent variables and for appropriate modeling of covariance structures when observations are correlated across time.

Power Calculations. Because this is a pilot study, the primary emphasis will be on the acceptability and feasibility of the two arms; hence, power is limited to determine efficacy of the intervention. We used GPower⁵⁹ software to estimate the difference in proportions between the two groups, with respect to PrEP-LINKage, that could be detected with 80% power. Given 40 participants per group (total $n = 80$), one-tailed alpha = .05, and a proportion of 0.5 for the control group, we will have 80% power to detect a 0.26 difference in proportions between groups.

Ethical Considerations

This study will be conducted in accordance with all applicable government regulations and University of Arkansas for Medical Sciences research policies and procedures. This protocol and any amendments will be submitted and approved by the UAMS Institutional Review Board (IRB) to conduct the study.

Title: Linking High-Risk Jail Detainees to HIV pre-exposure Prophylaxis: PrEP-LINK

PI: [name]

Site: University of Arkansas for Medical Sciences

The informed consent process will include a detailed verbal description of the study by a study staff member. The study staff will ask participants a series of questions to ensure that the information contained in the consent form is clearly understood by the participants prior to consenting to participation. Study staff will emphasize that participation is voluntary. Potential subjects will participate in an item-by-item reading of the consent form with the study staff person.

The consent process will take place in a quiet and private room (either in a small conference room in the jail, Community Corrections and re-entry centers, or in a community location), and participants may take as much time as needed to make a decision about their participation. The consent process may also take place over the phone, Zoom, FaceTime, or other platform preferred by the participant to allow for social distancing during the Covid-19 pandemic. Participation privacy will be maintained and questions regarding participation will be answered. No coercion or undue influence will be used in the consent process.

In addition, we have a **Certificate of Confidentiality** from the National Institutes of Health. The purpose of this certificate is to protect the identity of research subjects participating in studies that collect sensitive information. Because this application proposes to collect detailed HIV sexual and substance use behavior among those with criminal justice system involvement, a Certificate of Confidentiality is necessary.

Dissemination of Data

Results of this study may be used for presentations, posters, or publications. The publications will not contain any identifiable information that could be linked to a participant.

Title: Linking High-Risk Jail Detainees to HIV pre-exposure Prophylaxis: PrEP-LINK

PI: [name]

Site: University of Arkansas for Medical Sciences

References

1. Mauer M. Addressing racial disparities in incarceration. *Prison J.* 2011;91(3_suppl):87S–101S.
2. Nellis A. The color of justice: Racial and ethnic disparity in state prisons. *Sentencing Proj Available Httpwww Sentencingproject Orgwp-Contentuploads201606-Color--Justice-Racial--Ethn-Disparity--State-Prisons Pdf* Accessed 22 Aug 2016. 2016.
3. *HIV Surveillance Report Arkansas, 2015.* Arkansas Department of Health; 2015. <http://www.healthy.arkansas.gov/programsServices/healthStatistics/Documents/STDSurveillance/HIV/AIDSAnnualReport.pdf>;2015. Accessed May 2, 2017.

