Primary outcomes will include acceptability and feasibility of the intervention, as well as PrEP uptake. Secondary outcomes will include adherence and retention in PrEP-related medical care at three, six and 12 months. Results will inform a subsequent multi-site RCT to test efficacy of the intervention in improving PrEP uptake, adherence, and retention in care among transitioning out of jail.

Between study aims 2 & 3 a total of 120 subjects will be consented with approximately 10 for aim 2 and 110 for aim 3.

NOTE: For this IRB application, we are only seeking approval for activities related to AIMs 2-3. AIM 1 was addressed in IRB #207297.

Study Design and Procedures

Human Subjects Involvement, Characteristics, and Design: Given the scope of inquiry and proposed project's aims, criminal justice (CJ) involved individuals are the human subjects of this project. Our research team understands that CJ-involved individuals represent a vulnerable population, as the correctional setting may be perceived as a coercive environment. Therefore, all research must be conducted with rigorous ethical standards and with numerous safeguards in place to protect participants. A 2006 Institute of Medicine report on research involving prisoners called for the following requirements:

- 1) a risk-benefit approach, whereby the potential benefits of the research to the prisoners outweigh the potential risks;
- 2) research should be conducted with "collaborative responsibility," referring to the idea that the design and implementation of the research should include the input of all relevant parties (including prisoners and correctional administrators);
- 3) voluntary informed consent must be obtained, and privacy maximized; and

Title: Linking High-Risk Jail Detainees to HIV pre-exposure Prophylaxis: PrEP-LINK

PI: [name]

Site: University of Arkansas for Medical Sciences

4) research must be monitored throughout the course of the study in order to verify compliance with approved protocols and to detect and report adverse events. The research plan described in this application complies with all of these requirements. Below each aim and the relevant human participants' involvement, characteristics and design are described.

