There will be two groups that participants can be assigned to if they choose to participate in the study. Each person will be randomly assigned to one of these groups. One group will provide information about PrEP and HIV prevention and referral to PrEP clinics in the community. The second group will be the same as the first group but will also provide access to a CHW who will assist them with getting to a PrEP clinic and also helping them with other needs they may have.

A member from the study team will review the informed consent documents with the prospective participants and ask them questions to make sure they are eligible to participate in this study (PrEP-LINK eligibility and demographic screening form). Their responses to the prescreen form will not be shared with anyone outside of the study and will not contain any identifying information. They will be kept completely private, and will be in a password protected, encrypted database on a secured server at UAMS that can only be accessed by designated study staff.

Before we collect this information, we ask that participants provide their name so that we can assign a 9-digit study-ID number to de-identify their responses. Names will be stored separately from responses in locked filing cabinet in a secured office and will never be connected. At the end of the study, the link between the name and the study ID will be permanently destroyed.

Random Assignment to Study Condition. Once qualified for the study, we will randomly assign them to one of the two study groups. Once assigned to a group, after the completion of the

Table 4: Points of Contact for each Assessment for Aims 2 and 3

Type of Visit	Assessment	Location
Eligibility Screen	Education and Screening for initial PrEP indication including HIV rapid testing or self-report of recent negative HIV test within correctional facility	Pulaski County Jail, Central Arkansas Community Corrections Center, East Central Arkansas Community Corrections Center, Hidden Creek Opportunity Center, Quality Living Center, Better Community Development, Inc.
Consent, Enrollment	Baseline Research Assessment	CED Core community site
Presentation at PrEP Program for PrEP prescription dispensed	Baseline Research Assessment	Community based PrEP Provider
PrEP intervention sessions	Adherence assessment (self-report only), sexual risk ACASI, post-incarceration issues and HIV risk only	Community based PrEP provider or CED Core Community site

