Title: Linking High-Risk Jail Detainees to HIV pre-exposure Prophylaxis: PrEP-LINK

PI: [name]

Site: University of Arkansas for Medical Sciences

Short-term follow up assessment	Full assessment battery, including adherence assessment (self-report and clinical chart abstraction)	CED Core community site
Long-term follow up assessment	Full assessment battery, including adherence assessment (self-report and clinical chart abstraction)	CED Core community site

baseline data collection measures the study research assistant will inform the community health worker and the participant to what group they were assigned to.

The participants will take place in the following activities over the course of 12 months:

- An HIV test using the FDA-approved OraQUICK ADVANCE® Rapid HIV Antibody Tests or self-report of recent (within 12 months) HIV test within correctional facility.
 - If HIV rapid testing is completed during eligibility screening visit, during the testing process the participant will receive:
 - (1) Pre-test counseling: A member of the research team, who has been trained by the Arkansas Department of Health to perform HIV counseling, will provide information on HIV and the meanings of a positive and negative test. Participants will have an opportunity to ask questions and will be offered prevention counseling.
 - (2) HIV testing: To test for HIV, a member of the research team will use the FDA approved OraQUICK ADVANCE® Rapid HIV Antibody Test.
 - (3) Post-test counseling: They will find out the results of their HIV test about 20 minutes after being tested. A member of the research team will go over the results of the test and engage in routine post-test counseling.
 - If tested positive for HIV, we will refer to the Arkansas Health Department for confirmatory testing and medical care. Study staff will also follow up to see if they received a confirmatory test. Additionally, any information collected up to that point will be destroyed and their participation in the study will be complete.
 - All participants will receive:
 - (4) PrEP counseling: Following screening and after the completion of the baseline assessment survey, participants will receive information about PrEP using materials developed by the Centers for Disease Control and Prevention (CDC). This includes a brochure that lists local clinics where PrEP is available and how to make an appointment.

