Maintaining Contact. Because the study will take place over about 12 months after the participant's enrollment date, it will be important for us to be able to keep in contact with them. During each visit, we will ask for information that will help us contact them in the community in order to schedule study related appointments. We will ask for many ways to try to reach the participant's in case their phone number is disconnected or changed. We will contact them regularly to update your contact information. Participants will be considered to have missed a 6 or 12 month assessment 60 days after the target assessment date, and will be eligible 30 days before target assessment date. Research staff will make at least 3 contact attempts to reach participants for the 3 month and 9 month locator check in, with the goal of updating contact information.

Study Population

Participants will be enrolled in the proposed PrEP-LINK intervention who are HIV-uninfected and detained in the Pulaski County jail or individuals who are within 30 days of having been released from a correctional setting. We will work with jail staff to identify individuals who are within 2 weeks of discharge and will conduct screenings among these individuals to determine study eligibility. We will also work with Central Arkansas Community Corrections and local re-entry centers to identify individuals who have been released from incarceration within 30 days. Because many types of HIV related risks are present in this population (e.g. MSM or PWID), we will recruit participants from the following groups: MSM, PWID and heterosexual non-substance users (more participants may be enrolled, as needed). For the final two categories, (PWID and heterosexuals), we will recruit equal numbers of men and women. The recruitment will be completed when 120 individuals have been consented to have 100 participants complete the protocol.

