- 4) HIV negative confirmed through an on-site rapid HIV test or self-reported recent (within 12 months) negative HIV test within a correctional facility
- 5) Recently released from the Pulaski County Regional Detention Facility into the community and not into another detention facility or recently released (within 30 days) from a correctional facility and residing in Central Arkansas.
- 6) At substantial risk for HIV as determined by CDC/WHO PrEP guidelines, which includes engaging in any of the following behaviors in the last six months:
 - Having condomless vaginal or anal sex with more than one partner,
 - Having a sex partner with one or more HIV risk (e.g. PWID, a sex worker),
 - Being diagnosed with a STI,
 - Reporting history of sharing injection material/equipment, or
 - Having a sexual partner who is HIV positive.

Exclusion Criteria

Potential participants unable to provide informed consent, including people with severe mental illness requiring immediate treatment or with mental illness limiting their ability to participate (e.g., dementia), will be excluded.

Risks and Benefits

While the risks related to human subjects' participation in this study are minimal, we acknowledge that the possibility of harm to participants does exist. We recognize that participants will be asked to provide potentially sensitive information (including illicit substance use and sexual risk behaviors and criminal justice involvement) and therefore may experience discomfort, anxiety, or stress in responding to certain study questions. As such, as part of the informed consent procedure, participants will be advised that their answers will be confidential, and issues discussed will in no way impact their criminal justice status, nor ability to obtain or be referred to medical care or social services. At the start of the interview, participants will be informed that they can skip and refuse to answer any questions that they may find uncomfortable or embarrassing.

The potential benefits to participants include reduction in risk of HIV acquisition with use of pre-

Title: Linking High-Risk Jail Detainees to HIV pre-exposure Prophylaxis: PrEP-LINK

PI: [name]

Site: University of Arkansas for Medical Sciences

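### Randomisation method is not described, and recruitment setting should be a pre-specified term in the PrEP uptake model rather than left to a baseline significance test

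*Combined protocol and SAP*

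**What the plan says.** The paragraph headed Random Assignment to Study Condition is essentially the whole description of the method: "Once qualified for the study, we will randomly assign them to one of the two study groups". Sequence generation, allocation ratio, blocking, stratification and concealment are not mentioned. Equal arms appear only as an assumption under Power Calculations ("Given 40 participants per group").

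The numbers are "approximately 10 for aim 2 and 110 for aim 3", with recruitment ending when "120 individuals have been consented to have 100 participants complete the protocol".

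Study Population admits people "detained in the Pulaski County jail or individuals who are within 30 days of having been released from a correctional setting". It also sets recruitment groups by HIV-risk route, and for two of them says "we will recruit equal numbers of men and women". Those are targets for who is recruited; nothing ties them to how arms are assigned.

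Data Analysis covers imbalance in two steps. Baseline variables are compared between arms (Fisher's exact test for dichotomous ones) with significance at 0.05 or below, and any variable not equally distributed is then added to the regression models. The regression models are also to be informed by bivariate analyses. Recruitment setting is not named as a covariate.

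**The concern.** In a trial of about 110 people, arms can differ by chance in size and in the mix of people recruited in jail and in the community. If setting predicts PrEP uptake, that imbalance adds noise to the one comparison meant to give preliminary evidence of efficacy. Setting is a plausible predictor: PrEP is prescribed only at a community clinic, so anyone randomised while still detained cannot start until release. It is also already known, because the route of entry is part of eligibility.

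The planned handling is the weak part. A significance test asks whether imbalance exceeds chance, which is not the question after randomisation; what matters is whether the variable predicts the outcome. At this size the test also has a coarse threshold. Choosing covariates after seeing the arms is harder to defend than a model fixed beforehand. At stake is a small amount of precision and a cleaner analysis, not the validity of the trial.

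**Working it through.** **Inputs.** From the protocol: about 110 randomised (Aim 3); 40 per group, one-tailed 0.05, control uptake 0.50 and difference 0.26 (Power Calculations); two-tailed tests at 0.05 (Data Analysis). Assumed, because the protocol gives no figures: half recruited from jail (30% as a variant); uptake gap between settings of 10, 20 or 30 points; simple 1:1 randomisation as the comparator.

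**1. The plan's own figure.** Pooled z test, 40 per group, 0.50 v 0.76. Standard error under the null: √(2 × 0.63 × 0.37 / 40) = 0.1080. Under the alternative: √((0.25 + 0.1824) / 40) = 0.1040. Power = Φ((0.26 − 1.645 × 0.1080) / 0.1040) = Φ(0.79) = 78.6%. The detectable difference at 80% is 0.265, so the stated 0.26 reproduces to rounding. With the two-tailed test actually planned and 55 per group, the same formula gives 81.5%, the reference level below.

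**2. Arm sizes.** Binomial(110, 0.5): the 95% range for one arm is 45 to 65, and the arms differ by 10 or more with probability 39%. The consequence is slight: variance rises by 0.9% on average, about 0.3 points of power.

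**3. Imbalance in setting.** SD of the difference in jail share = √(0.5 × 0.5 × 4 / 110) = 9.5 points.
- P(10 points or more) = about 29%.
- A test at 0.05 flags at about 1.96 × 9.5 = 18.7 points. P(19 points or more) = about 4.5%.
- So about 29 − 4.5 = 25% of trials have a difference of 10 to 19 points that the test does not flag. Fisher's exact test is stricter still: with 55 per arm, 33 v 22 from jail (20 points) gives p = 0.056.

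**4. Effect on the estimate.** At a 20-point gap, imbalance moves the uptake difference by 0.20 × 9.5 = 1.9 points SD (95% within about 3.7), against a standard error of about 9 points.

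**5. Equivalent participants.** With half from jail and mean uptake 0.50, the within-setting variance ratio is 1 − (gap/2)² / 0.25 = 0.99, 0.96, 0.91. Then 110 / ratio − 110 = 1.1, 4.6, 10.9.

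**6. Power.** Simulation, 40,000 runs per scenario, N = 110, two-sided, effect 0.26; adjusted analysis by Mantel-Haenszel.

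| Jail share, gap | Simple, unadjusted | Simple, adjusted | Stratified, adjusted |
|---|---|---|---|
| 50%, 10 points | 81.4% | 81.2% | 81.7% |
| 50%, 20 points | 81.8% | 82.9% | 83.7% |
| 50%, 30 points | 81.8% | 85.5% | 86.3% |
| 30%, 30 points | 81.5% | 84.4% | 85.6% |

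With half from jail, the full gain from first to last column is about 0.3, 2.0 and 4.5 points (before rounding). Adjustment alone gives about −0.2, 1.1 and 3.8; stratifying then adds 0.5, 0.9 and 0.8.

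**7. Type I error.** Half from jail, simple randomisation, unadjusted: 4.8 to 4.9%. Stratified and adjusted: 4.7 to 4.9%. Stratified but not adjusted: 4.5, 4.1 and 3.7% at the three gaps, so stratifying without adjusting makes the test conservative.

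**The case against.** The best case for leaving the plan alone has five parts.

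- **Silence is not a design.** A reader might infer that the trial uses unrestricted randomisation. The text does not say that; equal groups in the power sentence fit blocking just as well. This stands: the defect is an undescribed method.
- **Different access to PrEP is an inference.** A reader might take jail and community recruits to have different access. Everyone receives the same counselling ("This includes a brochure that lists local clinics where PrEP is available and how to make an appointment"). Inclusion criterion 5 requires jail recruits to be "Recently released from the Pulaski County Regional Detention Facility into the community and not into another detention facility", and Table 4 puts consent and enrolment at a community site. Against that, the narrative inclusion criteria admit people currently in the jail, and Ethical Considerations allows consent in a jail conference room. The documents conflict, so the access argument is possible but not established. Even for those enrolled in jail, screening is aimed at people within 2 weeks of discharge, which bears more on time-to-uptake than on uptake over 12 months.
- **The gain is small.** This stands, above all for stratification, which adds under 1 point of power once the analysis adjusts.
- **Imbalance is already handled.** Only partly. Read literally, any inequality in proportions triggers adjustment; read with the stated 0.05 threshold, most imbalances do not. On either reading the model depends on the data, and setting is not named.
- **Blocking has a cost here.** The community health worker who delivers the intervention also conducts eligibility screening and is told assignments, so the ends of blocks could be guessed. This stands, and concealment has to be part of any change.

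**Conclusion.** The point holds as a low-cost improvement. The randomisation method is not described, and the only stated response to chance imbalance is a data-driven rule that omits recruitment setting and, at its 0.05 threshold, misses most imbalances of 10 to 19 points.

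It does not support a stronger reading. The uptake comparison is unbiased, type I error is not inflated, and the documents show neither unrestricted randomisation nor a difference in uptake by setting. The pilot also states that its main emphasis is acceptability and feasibility and that power for efficacy is limited.

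With 110 people and half from jail, the gain ranges from almost nothing at an assumed 10-point gap to 4.5 points of two-sided power at 30 points. At 20 to 30 points most of it comes from adjustment. These sizes rest on the assumed gap, jail share and simple randomisation. If setting does not predict uptake, the gain disappears and the loss from adjusting is negligible.

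**What to change.** 1. In Data Analysis, state that recruitment setting (jail v community corrections or re-entry) enters the PrEP uptake model as a fixed term whatever the baseline comparisons show, or that the primary estimate is a Mantel-Haenszel risk difference by setting. Let this replace the test-then-adjust rule for the uptake analysis.
2. In Random Assignment to Study Condition, state 1:1 assignment from a pre-generated list, stratified by setting, in permuted blocks of randomly varying size. Say who holds the list, and that the community health worker and other recruiting staff cannot see it. Add no strata beyond setting and, at most, risk group.
3. Reconcile the passages on whether jail recruits are enrolled before or after release, so that setting is defined at a fixed point before assignment.

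The cost is a few sentences and one list, with no extra participants or staff. The downside is some predictability at block ends, limited by varying block sizes and concealment. If the sponsor prefers to leave the sequence unstratified, the first item alone secures most of the gain at gaps of 20 to 30 points.
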